5.2. Exclusion Criteria

Any potential participant who meets any of the following criteria will be excluded from participating in the study:

PsA and **Psoriasis**

- 1. Has other inflammatory diseases that might confound the evaluations of benefit of guselkumab therapy in the treatment of PsA, including but not limited to rheumatoid arthritis, ankylosing spondylitis/non-radiographic axial spondyloarthritis (note: this does not include a primary diagnosis of PsA with spondylitis), systemic lupus erythematosus, or Lyme disease (confirmed by Western blot).
- 2. Has received more than 1 prior anti-TNF α agent (or biosimilars).
- 3. Has received an anti-TNF α agent within the following timeframes:
 - Infliximab (or its biosimilars) or golimumab (IV), within 8 weeks prior to the first administration of study intervention.
 - Golimumab SC, adalimumab or certolizumab pegol (or their biosimilars), within 6 weeks prior to the first administration of study intervention.
 - Etanercept (or its biosimilars) within 4 weeks prior to the first administration of study intervention.
- 4. Has previously received any biologic treatment other than an anti-TNFα agent including, but not limited to, guselkumab, ustekinumab, secukinumab, tildrakizumab, ixekizumab,brodalumab, risankizumab or other investigative biologic treatment.
- 5. Has ever received Janus kinase (JAK) inhibitor including but not limited to tofacitinib, baricitinib, filgotinib, peficitinib, decernotinib, upadacitinib or any other investigational JAK inhibitor.
- 6. Has received any systemic immunosuppressants (eg, azathioprine, cyclosporine, 6-thioguanine, mercaptopurine, mycophenolate mofetil, hydroxyurea, tacrolimus) within 4 weeks prior to the first administration of study intervention.

- 7. Has received apremilast within 4 weeks prior to the first administration of study intervention.
- 8. Has received non-biologic DMARDs other than MTX, SSZ, HCQ, LEF, within 4 weeks prior to the first administration of study intervention.
- 9. Is receiving 2 or more non-biologic DMARDs specified in Table 3 at baseline.
- 10. Has a nonplaque form of psoriasis (eg, erythrodermic, guttate, or pustular).
- 11. Has current drug-induced psoriasis (eg, a new onset of psoriasis or an exacerbation of psoriasis from beta blockers, calcium channel blockers, or lithium).
- 12. Has received phototherapy or any systemic medications/treatments that could affect psoriasis evaluations (including, but not limited to, retinoids, 1,25-dihydroxy vitamin D3 and analogues, psoralens, fumaric acid derivatives, with the exception of those in Table 3) within 4 weeks of the first administration of study intervention.
- 13. Has used topical medications/treatments that could affect psoriasis evaluations (including, but not limited to, topical or intralesional injection of corticosteroids, anthralin, calcipotriene, topical vitamin D derivatives, retinoids, tazarotene, methoxsalen, trimethylpsoralens, pimecrolimus, tacrolimus, or topical traditional Taiwanese, Korean, or Chinese medicines) within 2 weeks of the first administration of any study intervention. Low potency topical corticosteroids on the face or groin are allowed at any time.
- 14. Has received epidural, intra-articular, intramuscular (IM), or IV corticosteroids, including adrenocorticotropic hormone during the 4 weeks prior to the first administration of study intervention.
- 15. Has received lithium within 4 weeks of the first administration of study intervention.
- 16. Has received an experimental antibody or biologic therapy (other than those listed everywhere else in this section) within 6 months prior to the first administration of study intervention, or received any other experimental therapy, including an investigational medical device, or new investigational agent within 3 months or 5 half-lives (whichever is longer) prior to the first administration of study intervention or is currently enrolled in another study using an investigational intervention or procedure.

Coexisting medical conditions or past medical history

17. Has a history or current signs or symptoms of severe, progressive, or uncontrolled renal, hepatic, cardiac, vascular, pulmonary, gastrointestinal, endocrine, neurologic, hematologic, rheumatologic (with the exception of PsA), psychiatric, genitourinary, or metabolic disturbances.

- 18. Has unstable cardiovascular disease, defined as a recent clinical deterioration (eg, unstable angina, rapid atrial fibrillation, or transient ischemic attack) in the last 3 months prior to screening or a cardiac hospitalization within the last 3 months prior to screening.
- 19. Currently has a malignancy or has a history of malignancy within 5 years prior to screening (with the exception of a nonmelanoma skin cancer that has been adequately treated with no evidence of recurrence for at least 3 months prior to the first study intervention administration or cervical carcinoma in situ that has been adequately treated with no evidence of recurrence for at least 3 months prior to the first study intervention administration).
- 20. Has a history of lymphoproliferative disease, including lymphoma; a history of monoclonal gammopathy of undetermined significance; or signs and symptoms suggestive of possible lymphoproliferative disease, such as lymphadenopathy or splenomegaly.
- 21. Is currently undergoing or has previously undergone allergy immunotherapy for a history of anaphylactic reactions.
- 22. Has a transplanted organ (with exception of a corneal transplant >3 months prior to the first administration of study intervention).
- 23. Has known hypersensitivity to any biologic medication, or known allergies or clinically significant reactions to murine, chimeric, or human proteins, mAbs, or antibody fragments.
- 24. Has unstable suicidal ideation or suicidal behavior in the last 6 months, that may be defined as an electronic Columbia-Suicide Severity Rating Scale (eC-SSRS) rating at screening of:
 - Ideation level 4: Some intent to act, no plan; OR
 - Ideation level 5: Specific plan and intent; OR
 - Any of the following suicidal behaviors:
 - Actual suicide attempts
 - Interrupted attempts
 - Aborted attempts
 - Preparatory actions

AND

is confirmed to be at risk by the investigator based on an evaluation by a mental health professional. The final decision on excluding a participant will be made at the judgment of the investigator.

- 25. Has known allergies, hypersensitivity, or intolerance to guselkumab or its excipients (refer to the IB).
- 26. Is pregnant, nursing, or planning a pregnancy (both men and women) within 12 weeks after receiving the last administration of study intervention.
- 27. Has had major surgery (eg, requiring general anesthesia and hospitalization) within 8 weeks prior to screening, or will not have fully recovered from such surgery, or has such surgery planned during the time the participant is expected to participate in the study (52 weeks). Note: Participants with planned surgical procedures to be conducted under local anesthesia may participate.
- 28. Is known to have had a substance abuse (drug or alcohol) problem within the previous 12 months prior to the first administration of study intervention.

Infections or predisposition to infections

- 29. Has a history of chronic or recurrent infectious disease, including but not limited to chronic renal infection, chronic chest infection (eg, bronchiectasis), recurrent urinary tract infection (eg, recurrent pyelonephritis or chronic non-remitting cystitis), fungal infection (eg, mucocutaneous candidiasis), or open, draining, or infected skin wounds or ulcers.
- 30. Has a history of an infected joint prosthesis or has ever received antibiotics for a suspected infection of a joint prosthesis, if that prosthesis has not been removed or replaced.
- 31. Has or has had a serious infection (eg, sepsis, pneumonia, or pyelonephritis) or has been hospitalized or received IV antibiotics for an infection within 2 months prior to screening.
- 32. Has or has had a herpes zoster infection within 2 months before screening.
- Has received, or is expected to receive, any live virus or bacterial vaccination within 3 months prior to the first administration of study intervention.
- 34. Has had a BCG vaccination within 12 months of first administration of study intervention.
- 35. Has a history of active granulomatous infection, including histoplasmosis, or coccidioidomycosis, before screening. Refer to Inclusion Criterion 13 for information regarding eligibility with a history of latent TB.

- 36. Has a chest radiograph within 3 months prior to the first administration of study intervention that shows an abnormality suggestive of a malignancy, significant cardiovascular or pulmonary disease or current active infection, including TB.
- 37. Has ever had a nontuberculous mycobacterial infection or opportunistic infection (eg, cytomegalovirus, pneumocystis, aspergillosis).
- 38. Has persistently indeterminate (indeterminate on repeat sampling) QuantiFERON-TB test results. Indeterminate results should be handled as described in Section 8.2.12.
- 39. Is infected with HIV (a confirmed positive serology for HIV antibody).
- 40. During the 6 weeks prior to baseline, have had ANY of
 - a) confirmed severe acute respiratory syndrome coronavirus 2 (SARS-CoV-2)/COVID 19 infection (test positive), **OR**
 - b) suspected SARS CoV 2 infection (clinical features without documented test results), **OR**
 - c) close contact with a person with known or suspected SARS -SoV 2 infection.

An exception to this criterion maybe granted if a participant has a documented negative result for a validated SARS-CoV-2 test:

- Obtained at least 2 weeks after conditions (a), (b), (c) above (timed from resolution of key clinical features if present, eg, fever, cough, dyspnea)

AND

- with absence of ALL conditions (a), (b), (c) above during the period between the negative test result and the baseline study visit.

NOTES on COVID-related exclusion:

• The field of COVID-related testing (for presence of, and immunity to, the SARS-CoV-2 virus) is rapidly evolving. Additional testing may be performed as part of screening and/or during the study if deemed necessary by the investigator and in accordance with current regulations / guidance from authorities / standards of care.

Precaution: for those who may carry a higher risk for severe COVID-19 illness, follow guidance from local health authorities when weighing the potential benefits and risks of enrolling in the study, and during participation in the study.

41. Tests positive for hepatitis B virus (HBV) infection (see Appendix 4 in Section 10) or is seropositive for antibodies to hepatitis C virus (HCV) at screening, unless the participant meets 1 of the following conditions:

- i. Has a history of successful treatment (defined as being negative for HCV RNA at least 12 weeks after completing antiviral treatment) and has a negative HCV RNA test result at screening, OR
- ii. While seropositive has a negative HCV RNA test result at least 12 weeks prior to screening and a negative HCV RNA test result at screening.

General

- 42. Is unable or unwilling to undergo multiple venipunctures because of poor tolerability or lack of easy access to veins.
- 43. Lives in an institution on court or authority order.
- 44. Has any condition that, in the opinion of the investigator, would make participation not be in the best interest (eg, compromise the well-being) of the participant or that could prevent, limit, or confound the protocol-specified assessments.
- 45. Is an employee of the investigator or study site, with direct involvement in the proposed study or other studies under the direction of that investigator or study site, as well as family members of the employees or the investigator.
- 46. Is an employee of the Sponsor.

NOTE: Investigators should ensure that all study enrollment criteria have been met at screening. If a participant's clinical status changes (including any available laboratory results or receipt of additional medical records) after screening but prior to the first dose of study intervention is given such that the participant no longer meets all eligibility criteria, then the participant should be excluded from participation in the study, Section 5.4, describes options for retesting. The required source documentation to support meeting the enrollment criteria are noted in Appendix 10.5.

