5. STUDY POPULATION

Screening for eligible participants will be performed within approximately 6 weeks before administration of the study intervention. Refer to Section 5.4, Screen Failures for conditions under which the repeat of any screening procedures may be allowed.

The inclusion and exclusion criteria for enrolling participants in this study are described below. If there is a question about these criteria, the investigator must consult with the appropriate Sponsor representative and resolve any issues before enrolling a participant in the study. Waivers are not allowed.

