- d. Within 8 weeks before the first administration of study intervention, have a negative QuantiFERON®-TB test result, or have a newly identified positive QuantiFERON-TB test result in which active TB has been ruled out and for which appropriate treatment for latent TB has been initiated before the first administration of study intervention.
 - **NOTE:** A negative tuberculin skin test result is required if the QuantiFERON-TB test is not approved/registered in the country in which this protocol is being conducted. The frequency of TB testing can be increased depending on local health authority requirements. In Ukraine, while the QuantiFERON-TB test is not approved/registered, it is acceptable, and an additional tuberculin skin test is not required. The QuantiFERON-TB test and the tuberculin skin test are not required at screening for participants with a history of latent TB, if active TB has been ruled out, and if appropriate treatment has been initiated/completed as described above in Inclusion Criterion 13a.
- e. Have a chest radiograph (both posterior-anterior and lateral views, or per country regulations where applicable), taken within 12 weeks before the first administration of study intervention and read by a radiologist or qualified pulmonologist, with no evidence of current, active TB or old, inactive TB. A chest CT scan is also acceptable if already available or obtained outside of the study protocol. Participants with persistently indeterminate QuantiFERON-TB test results may continue without treatment for latent TB if active TB is ruled out, their chest radiograph shows no abnormality suggestive of TB (active or old, inactive TB) and the participant has no additional risk factors for TB as determined by the investigator. This determination must be promptly reported to the medical monitor or designee and recorded in the participant's source documents and initialed by the investigator.
- 14. Agree not to receive a live virus or live bacterial vaccination during the study, or within 12 weeks after the last administration of study intervention.
- 15. Agree not to receive a Bacillus Calmette-Guérin (BCG) vaccination during the study, and within 12 weeks after the last administration of study intervention.

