8.2.12. Tuberculosis Evaluations

8.2.12.1. Initial Tuberculosis Evaluation

Participants must undergo testing for TB (refer to Appendix 10.3) and their medical history assessment must include specific questions about a history of TB or known occupational or other personal exposure to individuals with active TB. The participant should be asked about past testing for TB, including chest radiograph results and responses to tuberculin skin or other TB testing. Investigators have the option to use both the QuantiFERON-TB test and the tuberculin skin test to screen for latent TB if they believe, based on their judgment, that the use of both tests is clinically indicated to evaluate a participant who is high risk of having latent TB. If either the QuantiFERON-TB test or the tuberculin skin test is positive, the participant is considered to have latent TB infection for the purposes of eligibility for this study.

Participants with a negative QuantiFERON-TB test result (and a negative tuberculin skin test result in countries in which the QuantiFERON-TB test is not approved/registered or the tuberculin skin is mandated by local health authorities) are eligible to continue with pre-randomization procedures. Participants with a newly identified positive QuantiFERON-TB test result must undergo an evaluation to rule out active TB and initiate appropriate treatment for latent TB. Appropriate treatment for latent TB is defined according to local country guidelines for immunocompromised patients. If no local country guidelines for immunocompromised patients exist, US guidelines should be followed, or the participant will be excluded from the study.

A participant whose first QuantiFERON-TB test result is indeterminate should have the test repeated. In the event that the second QuantiFERON-TB test result is also indeterminate, the participant may be enrolled without treatment for latent TB if active TB is ruled out, their chest radiograph shows no abnormality suggestive of TB (active or old, inactive TB) and the participant has no additional risk factors for TB as determined by the investigator. This determination must be promptly reported to the Sponsor's or designee's medical monitor and recorded in the participant's source documents and initialed by the investigator.

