4.4. Per-Protocol Analysis Set (Week 0 – Week 24)

The Per-Protocol Analysis Set (PPAS) includes all participants in FAS who met all inclusion and exclusion criteria and had no major protocol deviations prior to Week 24 that could have impacted efficacy assessment per clinical judgement (Appendix 3). This analysis set will be used for the analyses of *selected* efficacy endpoints through Week 24. Participants to be excluded from this analysis will be identified prior to the Week-24 DBL and unblinding.

In the analyses for this set, participants will be analyzed according to the randomized study intervention they were **assigned to**, regardless of the study intervention they actually received.

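### Exclusion 38 conflicts with Inclusion 13e and Section 8.2.12.1 on whether some participants with two indeterminate QuantiFERON-TB results may enrol

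*Protocol*

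**What the plan says.** Exclusion 38 (Protocol 5.2) has two sentences. The first makes this finding an exclusion: "Has persistently indeterminate (indeterminate on repeat sampling) QuantiFERON-TB test results". The second is a cross-reference: "Indeterminate results should be handled as described in Section 8.2.12". The list is introduced by "Any potential participant who meets any of the following criteria will be excluded from participating in the study", so one criterion is enough to bar a participant.

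Two other places let the same participant in. Inclusion 13e (Protocol 5.1) says: "Participants with persistently indeterminate QuantiFERON-TB test results may continue without treatment for latent TB if active TB is ruled out". Section 8.2.12.1 says that, after a second indeterminate result, "the participant may be enrolled without treatment for latent TB if active TB is ruled out". Both add that the chest radiograph must show no abnormality suggestive of TB and that the investigator must find no additional TB risk factors. Both also require prompt reporting to the medical monitor.

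Inclusion 13d requires participants to "have a negative QuantiFERON®-TB test result, or have a newly identified positive QuantiFERON-TB test result", with further steps for the positive case. Its note exempts some participants with a history of latent TB from testing. It makes no provision for an indeterminate result.

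On the analysis side, SAP 4.4 says the Per-Protocol Analysis Set "includes all participants in FAS who met all inclusion and exclusion criteria" and had no major deviations before Week 24 that could have affected efficacy assessment in clinical judgement. SAP Appendix 3 lists entering without satisfying the criteria as a category of major deviation.

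**The concern.** Eligibility on a TB criterion should have one answer. Here a participant with two indeterminate results who meets the three conditions is barred by the first sentence of Exclusion 38 and admitted by 13e and 8.2.12.1. Two sites reading different passages may reach different decisions on identical patients. Protocol Section 2.3.1 names serious infection and reactivation of latent infection as a study risk and relies partly on TB exclusions to mitigate it.

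The statistical consequence is narrower. Per-Protocol membership depends on having met all eligibility criteria. If the criteria disagree, membership for these participants depends on which passage the classifier follows, and the SAP gives no rule for it.

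**Working it through.** The plan states no figure on this point, so the check is a comparison of the passages.

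**Step 1. Sort participants with two indeterminate results.**

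| Participant | Exclusion 38, first sentence | 13e and 8.2.12.1 | Conflict? |
|---|---|---|---|
| Fails at least one of the three conditions | Excluded | Permission not available | No |
| Meets all three conditions | Excluded | May continue or be enrolled | Yes |

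The conflict is confined to the second row.

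**Step 2. Test whether the cross-reference in Exclusion 38 settles it.** There are two readings.
- *Literal.* The first sentence bars the participant, and the pointer covers only procedure, such as the repeat of a first indeterminate test that 8.2.12.1 also describes. The permissions in 13e and 8.2.12.1 are then wrong.
- *Deferral.* The pointer hands the decision to 8.2.12. The first sentence of Exclusion 38 is then wrong for everyone in the second row.

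Either way, a stated eligibility rule has to change.

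**Step 3. Check 13d.** All inclusion criteria must be met. A tested participant whose result is indeterminate fits neither result that 13d accepts, yet 13e lets that participant continue. Criterion 13 is therefore inconsistent within itself, apart from Exclusion 38.

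**Step 4. Check Section 7.1.** For a participant undergoing TB evaluation, two indeterminate results on repeat testing are listed among the grounds for discontinuing study intervention, again with a pointer to 8.2.12. This concerns conduct on study, so it is not evidence about screening eligibility. It does need to agree with whatever rule is kept.

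**Step 5. Trace the analyses.**
- Primary analysis: Full Analysis Set, all randomized participants (SAP 4.2 and 5.3.4.3). Eligibility status plays no part.
- Main analyses of the major secondary endpoints: also the Full Analysis Set, with a skin-disease subset for IGA and PASI 90 (SAP 5.3.5).
- Per-Protocol set: for the primary endpoint, Sensitivity Analysis 3 only (SAP 5.3.4.4).

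**Step 6. Scale per participant.** The documents do not say how many participants are affected. For illustration, removing one participant with outcome x (1 = responder, 0 = non-responder) from a group of n with response rate p changes the rate by (p − x)/(n − 1). Take the planned n = 150 and the q8w rate of 44.4% from PSA3003 used in the sample-size section:
- removing a non-responder: 0.444/149 = +0.30 percentage points;
- removing a responder: (0.444 − 1)/149 = −0.37 percentage points.

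This gives the order of magnitude for each participant. It is not an estimate of the total effect.

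**The case against.** The strongest reply is that Exclusion 38, read whole, is not a flat bar. It delegates to Section 8.2.12, which sets out a detailed rule that 13e matches. The protocol also qualifies exclusions by bare cross-reference elsewhere: Exclusion 35 points to Inclusion 13 for participants with a history of latent TB. On that view, those who fail the conditions are excluded and the rest follow 8.2.12.

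This is a workable reading, and may be the intended one, but the text does not establish it. Exclusions 19, 22, 40 and 41 state their exceptions in words; Exclusion 38 does not. If deferral is meant, its first sentence still says the opposite for the participants at issue, and 13d still has no place for them.

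Other parts of the reply stand. Protocol Section 5 says "Waivers are not allowed", and a reader might infer that enrolment under 13e would be a prohibited waiver. It would not: a permission written into the protocol is not a waiver. The same section tells investigators to resolve questions about the criteria with the sponsor before enrolling, and each such determination goes to the medical monitor. There is thus a central step that could keep practice uniform, and the documents do not support saying that sites will differ, only that they may.

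**Conclusion.** The contradiction is in the current protocol text and should be corrected. It applies to participants with two indeterminate results who meet all three conditions; the others are barred on any reading.

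A reader might infer that anyone enrolled under 13e is necessarily an eligibility deviation and must leave the Per-Protocol set. That holds only on the literal reading of Exclusion 38. On the deferral reading the participant met the criteria. The clinical-judgement phrase in SAP 4.4 attaches, as worded, to protocol deviations, though a looser reading could also keep such a participant in. The supportable statement is that classification could go either way.

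Nor do the documents support a concern about the primary result. The primary analysis is independent of eligibility status, and for the primary endpoint only Sensitivity Analysis 3 can move. The total size cannot be given because no count is reported; it could be zero. The conclusion rests on the wording alone and assumes that no separate site instruction has already settled the question.

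**What to change.** 1. Reconcile Exclusion 38 with Inclusion 13d, Inclusion 13e and Section 8.2.12.1 so that one eligibility rule remains. If an exception is intended, state it in the criterion itself. Which rule to keep is the sponsor's clinical decision.
2. Check that the on-study wording in Section 7.1 on two indeterminate results is consistent with that rule.
3. State in the SAP or the deviation-classification document how any participants already enrolled with two indeterminate results are classed for the Per-Protocol set, and report how many there are. SAP 4.4 already requires Per-Protocol exclusions to be identified before the Week 24 database lock and unblinding, so this fits the existing timetable.

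The cost is wording in a protocol amendment plus one classification rule. Sample size and the primary analysis do not change.
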